## **CONVERSION TO OPEN HEART SURGERY**

Valve Academic Research Consortium (VARC)-2; Updated Standardized Endpoint Definitions for Transcatheter Aortic Valve Implantation (TAVI); 2012-10-09.

Conversion to open sternotomy during the TAVI procedure secondary to any procedure-related complications.

## **CORONARY OBSTRUCTION**

Valve Academic Research Consortium (VARC)-2; Updated Standardized Endpoint Definitions for Transcatheter Aortic Valve Implantation (TAVI); 2012-10-09.

Angiographic or echocardiographic evidence of a new, partial or complete, obstruction of a coronary ostium, either by the valve prosthesis itself, the native leaflets, calcifications, or dissection, occurring during or after the TAVI procedure.

## **DEVICE DEFICIENCY**

Inadequacy of a medical device with respect to its identity, quality, durability, reliability, safety or performance

NOTE: Device deficiencies include malfunctions, use errors, and inadequate labeling.

**DEVICE RELATED**

Events that occur as the direct result of the Medtronic CoreValve™ System (MCS) or CoreValve™ Evolut R System as it relates to delivery, placement, efficacy or durability; these may involve the implanted device or the delivery system components.

**DEVICE RELATED COMPLICATIONS**

Complications associated with the device as it relates to delivery, placement, efficacy or durability; these may involve the implanted device or the delivery system.

**EMBOLISM**

Free flowing blood clot or lesion material that is located in the systemic or pulmonary circulation that occurs in the absence of infection after the immediate perioperative period. Embolism may be manifested by a neurological event or a noncerebral embolic event.

**ENCEPHALOPATHY**

Altered mental state (eg., seizures, delirium, confusion, hallucinations, dementia, coma, psychiatric episode, etc.).

**ENDOCARDITIS**

**Implanted valve endocarditis:** Any infection involving an implanted valve. The diagnosis of *operated valvular endocarditis* is based on one of the following criteria:

- re-operation with evidence of abscess, paravalvular leak, pus, or vegetation confirmed as secondary to infection by histological or bacteriologic studies;
- autopsy findings of abscess, pus, or vegetation involving a replaced valve; or
- in the absence of reoperation or autopsy, meeting of the Duke Criteria for endocarditis.

**Infective endocarditis** is diagnosed based on Duke Criteria and necessitates 2 major criteria, or 1 major and 3 minor criteria, or 5 minor criteria

**Major criteria 1: Positive blood culture for infective endocarditis**

Typical microorganism consistent with infective endocarditis from 2 separate blood cultures, as noted below:

- Viridans streptococci, *Streptococcus bovis*, or HACEK group (*Haemophilus. Actinobacillus actinomycetemcomitans, Cardiobacterium hominis, Eikenella corrodens, Kingella* or
- Community-acquired *Staphylococcus aureus* or enterococci, in the absence of a primary focus

**-OR-**

Microorganisms consistent with infective endocarditis from persistently positive blood cultures defined as:

- Two positive cultures of blood samples drawn >12 hours apart, or
- All of 3 or a majority of 4 separate cultures of blood (with first and last sample drawn 1 hour apart)

**Major criteria 2: Evidence of endocardial involvement**

Positive echocardiogram for infective endocarditis defined as:

- oscillating intracardiac mass on valve or supporting structures, in the path of regurgitant jets, or on implanted material in the absence of an alternative anatomic explanation, or
- abscess, or
- new partial dehiscence of prosthetic valve

**-OR-**

- New valvular regurgitation (worsening or changing of pre-existing murmur not sufficient)

**Minor criteria 1: Predisposition:** predisposing heart condition or intravenous drug use

**Minor criteria 2: Fever:** temperature > 38.0° C (100.4° F)

**Minor criteria 3: Vascular phenomena:** major arterial emboli, septic pulmonary infarcts, mycotic aneurysm, intracranial hemorrhage, conjunctival hemorrhages, and Janeway lesions

**Minor criteria 4: Immunologic phenomena:** glomerulonephritis, Osler's nodes, Roth spots, and rheumatoid factor

**Minor criteria 5: Microbiological evidence:** positive blood culture but does not meet a major criterion as noted above or serological evidence of active infection with organism consistent with infective endocarditis

**Minor criteria 6: Echocardiographic findings:** consistent with infective endocarditis but do not meet a major criterion as noted above

#### EXPLANT

Removal of the investigational valve implant for any reason, including post-mortem.

#### HEMOLYSIS

A plasma free hemoglobin value > 40 mg/dL is considered to be hemolysis and a reportable adverse event.

- **Major hemolysis:** A plasma free hemoglobin value > 40 mg/dL that requires intervention (i.e. iron replacement, blood transfusion, folic acid administration, corticosteroids, Intravenous immunoglobulin G (IVIG) and/or surgery). Major hemolysis events will be considered to be serious adverse events.
- **Minor hemolysis:** A plasma free hemoglobin value > 40 mg/dL that does not require intervention.

#### INFECTION

Elevated body temperature (fever), and White Blood Count (WBC) > 12,000/ml, and Significant leftward shift on Differential.

#### MAJOR ADVERSE CARDIOVASCULAR AND CEREBROVASCULAR EVENTS (MACCE)

Defined as a composite rate of

- all-cause death
- myocardial infarction (MI)
- all stroke, and
- reintervention (defined as any cardiac surgery or percutaneous reintervention catheter procedure that repairs, otherwise alters or adjusts, or replaces a previously implanted valve)

#### MAJOR ADVERSE EVENT (MAE)

Major Adverse events include the following:

- MACCE
- Acute kidney Injury
- Cardiac tamponade
- Prosthetic valve dysfunction Cardiogenic shock
- Prosthetic valve endocarditis
- Life-threatening, disabling or major bleeding
- Major vascular complication
- Cardiac Perforation
- Valve malpositioning

### MITRAL REGURGITATION

Mitral valve incompetence resulting in backward flow of blood.

2008 Focused Update Incorporated into the ACC/AHA 2006 Guidelines for the Management of Patients with Valvular Heart Disease (published in the October 2008 issues of Journal of the American College of Cardiology and Circulation)

Classification of the Severity of Valve Disease in Adults			
Mitral Regurgitation			
	Mild	Moderate	Severe
Qualitative Angiographic grade Color Doppler jet area	1+ Small, central jet, < 4cm  or <20% LA area)	2+ Signs of > mild present but no criteria for severe MR	3-4+ Vena contracta with > 0.7cm with large central MR jet (area >40% of LA area) or with a wall-impinging jet of any size, swirling in LA
Doppler vena contracta width (cm)	< 0.3	0.3-0.69	≥ 0.70
Quantitative (cath or echo) Regurgitant volume (mL per beat)	< 30	30-59	≥ 60
Regurgitant fraction (%)	< 30	30-49	≥ 50
Regurgitant orifice area (cm  )	< 0.20	0.29 – 0.39	≥ 0.40
Additional essential criteria Left atrial size Left ventricular size			Enlarged Enlarged

### MITRAL STENOSIS

A narrowing, stiffening or stricture of the mitral valve.

2008 Focused Update Incorporated into the ACC/AHA 2006 Guidelines for the Management of Patients with Valvular Heart Disease (published in the October 2008 issues of Journal of the American College of Cardiology and Circulation)

Mitral Stenosis			
	Mild	Moderate	Severe
Mean Gradient (mmHg)	Less than 5	5-10	Greater than 10
Pulmonary artery systolic pressure (mmHg)	Less than 30	30-50	Greater than 50
Valve area (cm  )	Greater than 1.5	1.0-1.5	Less than 1.0

## MORTALITY

A serious adverse event that is classified by the following:

**All-cause mortality:** All deaths from any cause after a valve intervention. This includes all cardiovascular and non-cardiovascular deaths.

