##### Day 0 = day of index procedure (TAVI or SAVR):

- 30 days (- 7 days and + 14 days)
- 3 months (90 ± 14 days)
- 6 months (180 ± 30 days)
- 12 months (365 ± 30 days)
- 18 months (545 ± 60 days)
- 24 months (730 ± 60 days)
- 3 years (1080 ± 60 days)
- 4 years (1440 ± 60 days)
- 5 years (1800 ± 60 days)

All randomized subjects will complete long-term follow-up through at least 5 years. Based on clinical assessments or regulatory requirements, follow-up may be extended to up to 10 years post-index procedure. Upon completion of the final protocol visit (discontinuation) subject participation will be considered complete and the patient should then be followed per the local standard of care for their condition.

Note: For subjects where the Index Procedure is never attempted (eg. subject withdraws consent for the procedure but agrees to complete follow-up) follow-up intervals will be calculated from the 31st days post-randomization (i.e. the 1st day after the 30 day window from randomization to complete the Index Procedure).

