### *C.5.2 Reporting*

Investigators are required to keep records on “all relevant observations, including records concerning adverse device effects (whether anticipated or unanticipated)” [21 CFR 812.140; ISO 14155 (2011)]. Adverse event collection will begin from the point of trial enrollment to trial closure. All new or worsening (from baseline) adverse events and technical observations will be captured on the AE eCRF through the 24-month follow-up visit. It is the responsibility of the Investigator to assess the subject for adverse events and capture the required adverse event information on the AE eCRF.

Once a subject has completed their 24-month scheduled follow-up visit only serious adverse events, major adverse events, cardiovascular events, device-related adverse events, including device related technical observations, unanticipated adverse device effects (UADE) or unanticipated serious adverse device effects (USADE), all strokes (CVAs) and deaths will be required to be reported. Reference section C.5.1 Adverse Events for event definitions and criteria. Medtronic representatives or their designees will conduct monitoring visits to review source documentation and verify the complete and accurate capturing of adverse events.

The Investigator must also notify the responsible IRB/MEC regarding new and significant safety information and any event identified by Medtronic that requires expedited FDA, and/or local regulatory agency, reporting as serious, unexpected, and related to the investigational device. It is the responsibility of the investigator to ensure site specific IRB/MEC safety reporting requirements are met.

Medtronic Clinical will ensure all device-related adverse events and all procedure-related SAEs are processed according to internal policies and procedures. When necessary, Medtronic Field Assurance will respond to sites in writing with the findings related to the product experiences.

The general procedure for investigators reporting any adverse event is as follows:

- Report the event to Medtronic as soon as possible but no later than the timeframes outlined below. (At the time of Site Initiation, sites will be provided with the telephone and other applicable contact information of the appropriate Medtronic designee).
- Complete all sections of the Adverse Event eCRF.
- Each unique event/diagnosis must be documented separately.

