## C.6 Statistical Methods and Analysis

### C.6.1 Statistical Considerations and Analysis

This section describes the statistical considerations and analysis plans for the SURTAVI trial. The statistical analysis will be performed by the statistics department of Medtronic. As primary analysis all randomized subjects will be analyzed following the modified intention to treat (mITT) approach; ie. analyses will be conducted on the cohort of subjects who undergo an attempted trial treatment, analyzed according to the randomized assignment. A secondary analysis of key objectives will be performed according to the therapy actually received.

Roll-in subjects will not be included in the primary or secondary analysis; however, the data will be summarized separately with descriptive statistics.

All follow-up periods are defined as the number of days after the procedure date.

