#### C.6.4.2 Randomized Population

If the patient signs informed consent, meets all inclusion and none of the exclusion criteria, and the Heart Team determines the patient is suitable for randomization in the trial, then the subject is reviewed by the SURTAVI Screening Committee. If the subject is approved by the Screening Committee and the subject is enrolled/randomized to either TAVI or SAVR the subject is added to the randomized population. Within the randomized population three sub-populations are distinguished:

- Intention to treat (ITT) population - Subjects are reported according to the randomized assignment, SAVR or TAVI, regardless of what, if any, therapy was actually received
- Modified intention to treat (mITT) population - Randomized subjects in whom a procedure is attempted. Subjects who undergo an attempted trial treatment are reported according to the randomized assignment, SAVR or TAVI, regardless of what, if any, therapy was actually received. A procedure attempt is defined as when the subject is brought into the procedure room and any of the following have occurred: anesthesia administered, vascular line placed, TEE placed or any monitoring line placed
- Implanted population - population includes the mITT subjects who are actually implanted with either the investigational TAVI device or a surgical valve. Depending on context, subjects may be analyzed according to randomized treatment assignment or treatment actually received.

The primary analysis for the primary objective and most secondary objectives will use the mITT population. At the conclusion of the trial, an analysis using the ITT population will also be presented.

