#### C.6.5.2 Randomization, Sample Size and Analysis Plan

Randomization will follow a 1:1 (treatment:control) allocation ratio and be stratified by site and need for revascularization, using a blocked randomization scheme with blocks of randomly varying sizes. The sample size for the mITT population is 1600 subjects.

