#### Sample Size Justification

The assumed values  $\pi_T = \pi_C = 0.17$  are based on the data published by Iturra et al and CoreValve US Pivotal High Risk study results. As reported in the Iturra paper, the incidence of all-cause mortality at 30 days was 2.8% and the late all-cause mortality Kaplan-Meier rate at 24 months was 12.1%. The overall 24-month all-cause mortality rate was approximately 15%. STS score reported in the Iturra paper ( $5.6 \pm 1.1$ ,  $n=502$ ) was similar to the STS score for subjects currently enrolled in the SURTAVI study ( $5.6 \pm 1.4$ ,  $n=654$ ), and it is believed that the 24-month all-cause mortality rate in SURTAVI will be approximately 15% at 24 months. The major stroke rate was 3.2% for subjects who survived to 1 year in the CoreValve Pivotal High Risk study. The High Risk study enrolled a higher-risk population than SURTAVI, therefore, the major stroke rate in the High Risk study is adjusted downward, and it is believed the disabling stroke rate at 24 months would be approximately 2% in the SURTAVI study. Overall, the estimation of the all-cause mortality or disabling stroke rate at 24 months is 17%.

Although the pre-specified analysis methods are Bayesian, the sample size is guided by a standard frequentist non-inferiority power analysis. Under the assumptions of  $\pi_T = \pi_C = 0.17$ , non-inferiority margin  $\delta=0.07$ , 1:1 randomization,  $\alpha = 0.05$ , and power = 95%, the method of Farrington and Manning as implemented in PASS 2008 indicates that the required sample size for a single-look analysis is 1258. To allow for up to 6% dropout, 1339 subjects must be accrued. Furthermore, to compensate for power lost in a two-look group sequential analysis plan using Pocock-type alpha spending, the sample size would have to be increased by about 12.5%. This leads to an estimated sample size of 1531. Thus a sample size of 1600 mITT subjects should provide ample power for establishing non-inferiority in the primary hypothesis test.

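### As written, the supportive ITT analysis leaves out deaths and disabling strokes between randomization and procedure, and the plan does not settle whether ITT accompanies an interim non-inferiority claim

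*Combined protocol and SAP*

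**What the plan says.** **Populations.** C.6.1 and C.6.4.2 make mITT primary: randomized subjects in whom a procedure was attempted, analyzed as assigned. ITT in C.6.4.2 covers all randomized subjects as assigned, whatever treatment they had and even if they had none.

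**Mortality.** O.2, under Mortality, defines all-cause mortality as "All deaths from any cause after a valve intervention". This is a component of the primary endpoint.

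**Clock.** C.6.1 states: "All follow-up periods are defined as the number of days after the procedure date". C.4.9 says the same for visits and adds that, where the procedure is never attempted, "follow-up intervals will be calculated from the 31", that is, from day 31 after randomization. C.4.5 allows up to 30 days from randomization to procedure, and assignment is not blinded.

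**Stroke.** The disabling-stroke definition in O.2 has no post-procedure limit. The separate neurological-event entry in O.2 is confined to deficits appearing after anesthesia.

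**ITT timing.** C.6.4.2: "At the conclusion of the trial, an analysis using the ITT population will also be presented". C.6.7.2 places the primary-endpoint analysis on both ITT and mITT and mentions no delay. The Analysis Plan in C.6.5.2 allows non-inferiority to be declared and submitted at the interim, and mentions no ITT run.

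**Data collection.** C.5.2: "Adverse event collection will begin from the point of trial enrollment to trial closure". Enrollment is randomization (C.4.5).

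**The concern.** Patients and staff know the assignment while a subject can still leave the primary set by not reaching the procedure room. Who leaves, and at what risk, may differ by arm. ITT is the analysis that would show whether this matters, and it can do so only if it counts what happens to those who leave.

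The definition and the clock work against that. Taken literally, a subject who dies while waiting has no endpoint death, and neither does a subject who is never treated and dies a year later. Such subjects would stay in the ITT denominator as event-free, or their status would be decided ad hoc.

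The arms are also not symmetric before day 0. C.4.7.1 allows staged PCI at least 7 days before TAVI, whereas C.4.7.2 has CABG done together with SAVR. A stroke complicating a post-randomization staged PCI falls before the clock starts. A stroke complicating CABG does not.

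No other planned analysis fills the gap. The implanted set is a subset of mITT, an analysis by therapy received cannot include untreated subjects, and C.6.6 on missing data and sensitivity names no ITT analysis.

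**Working it through.** **1. The plan's own figure.** Inputs from the Sample Size Justification: 17% in each arm ("Overall, the estimation of the all-cause mortality or disabling stroke rate at 24 months is 17"), margin 0.07, alpha 0.05, power 95%. From C.6.5.2: "Randomization will follow a 1:1 (treatment:control) allocation ratio". Farrington-Manning, with rates under the null of 0.2105 and 0.1405:

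n per arm = [1.645·√(0.1405·0.8595 + 0.2105·0.7895) + 1.645·√(2·0.17·0.83)]² / 0.07² = 628.6, so 629 per arm and 1258 in total.

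Then 1258/0.94 gives 1339, and 1339/0.875 gives 1531. All three stated figures reproduce, with alpha one-sided. The point here does not change them.

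**2. What an ITT run to the letter would count.**

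| Event | O.2 definition | Clock | Counted? |
|---|---|---|---|
| Death while waiting for the procedure | excluded | before day 0 | no |
| Death after day 31, never treated | excluded if read literally | inside | no, or unclear |
| Disabling stroke while waiting | not excluded | before day 0 | no |
| Disabling stroke after day 31, never treated | not excluded | inside | yes |

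**3. Can this change the ITT answer?** The documents give no rate of unattempted procedures and no event rate in those subjects, so the counts below are assumptions. Method: Beta(1,1) priors, margin 0.07, threshold 0.971, final look, 800 attempted per arm. With SAVR at 136/800 (17%), TAVI wins with up to 162/800 (posterior 0.973) and fails at 163/800 (0.969). Start from that borderline mITT win and add unattempted subjects. As written here means that none of their events count.

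| Unattempted TAVI / SAVR | Their events TAVI / SAVR | ITT posterior as written | ITT posterior, all counted |
|---|---|---|---|
| 8 / 40 | 2 / 10 | 0.951 (no win) | 0.983 (win) |
| 8 / 40 | 4 / 4 | 0.951 (no win) | 0.949 (no win) |
| 40 / 40 | 20 / 4 | 0.982 (win) | 0.853 (no win) |
| 40 / 40 | 7 / 20 | 0.982 (win) | 0.998 (win) |

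Row 1: as written, 162/808 v 136/840, a difference of 3.9 points; all counted, 164/808 v 146/840, 2.9 points. Row 3: as written, 162/840 v 136/840, 3.1 points; all counted, 182/840 v 140/840, 5.0 points. The omission misleads against TAVI in row 1 and in its favor in row 3. In rows 2 and 4 it leaves the conclusion unchanged.

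**4. Shift in the difference (TAVI minus SAVR).** Let both arms be 17% in attempted subjects. If unattempted subjects count as event-free, the shift is 0.17 × (SAVR unattempted share − TAVI unattempted share). For 1% v 5% this is 0.17 × 0.04 = +0.68 points; for 2% v 10% it is 0.17 × 0.08 = +1.36 points, both against TAVI. Counting all their events, with the same shares and event rates of 17% to 50% in the unattempted, gives −3.3 points (0.10 × (0.17 − 0.50)) to +0.66 points (0.02 × (0.50 − 0.17)).

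**5. Timing.** Assume even accrual of 1600 mITT subjects over the 36 months in C.3.5. The interim falls near 36 × 1400/1600 + 12 = month 43.5, the last 24-month visit near month 60, and the last 5-year visit near month 96. If ITT waits for the final look, it follows an interim claim by about 16.5 months; if it waits for the end of follow-up, by about 52.5 months. The interim posterior itself was not recomputed, because the prediction model is not in the text available.

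**The case against.** Four points on the other side have force.

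- **The events are recorded.** Collection starts at randomization, every death must be reported (C.5.2.7), and the Clinical Events Committee adjudicates all deaths (C.5.3). A reader might infer that ITT is incapable of counting these events. The documents do not support that: this is a fault of definition and clock, and it can be repaired.
- **The O.2 phrase need not govern.** C.6.5 states the primary endpoint without it, and the ITT definition in C.6.4.2 includes subjects who received nothing. The day-31 note sits in the visit schedule. One can fairly say that time zero for ITT is unspecified. What remains is that the only rules stated, applied as they stand, give the wrong count and conflict with the ITT definition.
- **ITT may not be late.** A reader might infer that ITT is promised only years after the claim. C.6.4.2 does not say only, C.6.7.2 has no delay, and Section M uses the same expression for when the primary results are presented. The sections disagree; neither settles the matter.
- **Unseen text.** C.6.5.2 sends further analysis detail to the SAP, and the available text is part 2 of 4. An ITT rule may exist elsewhere.

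A reader might also want to attach a false non-inferiority rate. The documents give no basis for one. Such a rate would need assumed selection in one direction, and it would describe mITT exclusion, not events missing from ITT. Reporting ITT beside an unchanged mITT rule would leave it as it was.

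**Conclusion.** The point holds in a limited form. By its stated definition and clock, the ITT analysis of the primary endpoint omits deaths during a wait of up to 30 days and, read literally, later deaths in never-treated subjects. Disabling strokes during the wait are lost through the clock alone. Whether ITT accompanies an interim claim is left open by two sections that do not agree and by an interim rule that does not mention it.

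The size cannot be fixed from the documents. With assumed unattempted rates of 1–2% (TAVI) and 5–10% (SAVR), literal non-counting moves the ITT difference by 0.68 to 1.36 points against TAVI; with equal rates and more events in unattempted TAVI subjects, the omission favors TAVI. A borderline conclusion can flip either way or stay put. The uncertain direction is itself a reason to fix the rule before results are seen.

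The primary mITT analysis, the margin and the sample size are not at fault here. This should be fixed, with moderate confidence given the SAP detail not seen.

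**What to change.** 1. For ITT, set time zero at randomization and count every death and disabling stroke from then to 24 months, whether or not a valve intervention took place.
2. In O.2, remove the post-intervention qualifier from all-cause mortality, or confine it to procedural mortality. State that the neurological-event entry does not limit the stroke endpoint.
3. Reconcile C.6.4.2 with C.6.7.2 on when ITT is produced.
4. Add to C.6.5.2 that ITT, with the same margin and threshold, is reported beside mITT at both Win Looks and in any submission. mITT remains the basis of the decision.
5. Report the number unattempted by arm, with reasons and known outcomes.

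The cost is wording in the protocol and SAP and one extra analysis per look. There are no new visits and no change in sample size; events are already collected from enrollment, and C.4.9 already provides follow-up for untreated subjects who agree to it. The wording should be settled before the interim data are seen.
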